AH) Jacobs, S.E., et al., *Probiotic Effects on Late-onset Sepsis in Very Preterm Infants: A Randomized Controlled Trial.* Pediatrics. 2013, **132**: p.1055-1062.

In this double-blind, placebo-controlled, randomized trial, very preterm infants defined as born <32 weeks' gestation and weighing <1500g were supplemented soon after birth with either probiotics containing *St. thermophilus*, *B. Lactis* BB-12, and *B. infantis* BB-02 or placebo to determine the effect of the daily administration of probiotics on the incidence of definite late-onset sepsis. 1099 infants were enrolled with 548 randomized to the probiotic group and 551 to the control group. The study found no significant effect of the probiotic combination on definite late-onset sepsis in very preterm infants.

Al) Smith, T.J., et al., Effect of Lactobacillus rhamnosus LGG and Bifidobacterium animalis ssp. lactis BB-12 on health-related quality of life in college students affected by upper respiratory infections. Brit J Nutr. 2013, **109:** 1999—2007.

The aim of this study was to determine the effect of probiotics on the health-related quality of life in college students suffering an upper respiratory infection (URI). In this double-blinded, placebo-controlled trial, 231 healthy college students at Framingham State University were randomized to receive a daily dose (5g) of either strawberry-flavored probiotic powder or strawberry-flavored placebo powder. Each powder package contained 10 e 9 cfu of LGG and BB-12. The duration of URI's in the probiotic group was significantly shorter than the duration of the URI's of the control group. Also, the probiotic group had URI's of significantly lower severity compared to the placebo group.

AJ) Fox M, et al., Can probiotic yogurt prevent diarrhoea in children on antibiotics? A double-blind, randomised, placebo-controlled study. BMJ Open. 2015; **5**(1): e006474.

In this study, seventy-two children between the ages of 1-12 years prescribed broad-spectrum oral antibiotics were studied to examine the efficacy of yogurt containing *Lactobacillus rhamnosus GG* (LGG), *Bifidobacterium lactis* (Bb-12), and *Lactobacillus acidophilus* (La-5) in reducing the rate of antibiotic-associated diarrhea (AAD). Seventy children, thirty-six of whom received the pasteurized placebo yogurt and thirty-four of whom received the probiotic study yogurt, completed the trial, which consisted of consuming two 100g tubs of yogurt/day for the entire duration of the their antibiotic treatment. The probiotic group had significantly fewer instances of adverse events. Children in the probiotic group had fewer instances of diarrhea and no cases of severe diarrhea, compared to the placebo group.

4.1.6 Probiotics Treating and Preventing Antibiotic-Associated Diarrhea (AAD)

Acute diarrhea is commonly caused by infections or antibiotics. Children and adults are often placed on antibiotics and the rate of diarrhea associated with antibiotic usage is 20-35%, with 10-20% of the diarrhea due to *Clostridium difficile*.[41-49]

Antimicrobial resistance, stemming from antibiotic use, is a multifactorial problem. Major elements of the problem include over-prescription of antibiotics by physicians and poor compliance by patients.[50] Although educating physicians and the lay public has led to dramatic decreases in antibiotic prescriptions, approximately 25% of all visits for children under age five still results in a prescription for antibiotics.[48, 49, 51-53] In fact, children ages three to

36 months average over two antibiotic prescriptions per year, with nearly 30% receiving over four prescriptions per year.[49]

Probiotics have the potential to reduce the rate of AAD. Numerous meta-analyses have examined the potential role of probiotics, with the positive studies showing an effect size of 25-35%.[54-59] In a recent study, Correa et al. enrolled 80 children between six and 36 months of age who were receiving oral or parental antibiotic therapy. In addition to the antibiotics, infants were given either a combination of 10⁷ *B.lactis* and 10⁶ *S. thermophilus* or a placebo. In this study, 31% of the placebo group experienced diarrhea compared to 16% of the probiotic group (p, 0.044).[60] In a similar study, Arvola et al enrolled children on antibiotics and gave them either a matching placebo or LGG at 2x10¹⁰ CFU/day. After two weeks, 5% of the LGG group had diarrhea compared to 16% of the placebo group, with a treatment effect of -11% (95% confidence intervals of -21%, 0%).[61]

4.1.7 Functional Foods and Yogurt

Consuming foods to provide health benefits beyond basic nutritional needs is a well-accepted practice in the United States. For example, many parents feed their children cereal fortified with minerals and nutrients. Another example is the addition of folic acid to many food products; this has greatly decreased the incidence of neural tube defects in the U.S.[62, 63] Functional foods are enriched or enhanced foods that provide health benefits beyond the inherent nutritional value of the food.[64] For example, BENECOL® is a margarine type food proven in clinical trials to reduce LDL cholesterol.[65, 66] The promise of using functional foods to mitigate disease and promote health is one of the major reasons so many resources are being devoted to this exciting new field.[9, 67-70]

Yogurt is defined as milk fermented with two specific bacterial species, *L. bulgaricus* and *S. thermophilus*. To differentiate yogurt containing live and active cultures and those pasteurized after fermentation, the National Yogurt Association developed a seal, the Live Active Culture Seal. Any yogurt containing 10⁸ CFU/g at the time of manufacture may display this seal. A dose of probiotics of 10⁸-10¹⁰ cfu/day is the amount that has generally been studied and has resulted in health benefits. However, several surveys suggest the probiotic content of yogurt and probiotic supplements may be lower than labels would imply. Hamilton-Miller et al. examined 52 European probiotic products, including 11 yogurts, and found that none gave any indication of actual numbers and less than 50% accurately stated the bacterial species contained in the product.[71] This study highlights the lack of useful information available to consumers when selecting products containing probiotics.

Beniwal et al. studied the effect of yogurt containing *L. acidophilus* on AAD in an unblinded manner in hospitalized patients receiving oral or intravenous antibiotics. The 105 patients in the yogurt group received two 8-ounce vanilla yogurt containers for eight days. Yogurt supplemented with *L. acidophilus* decreased AAD from 24% to 12%.[72] However, the unblinded nature of this study makes these results only suggestive.

4.1.8 Summary and Significance

Bifidobacterium lactis strain BB-12 is a commercially available probiotic strain that has been used in a number of feeding and clinical trials.[73-84] BB-12 has been found to survive transit through the stomach, small intestine and colon.[85-87] Additionally, long term consumption of probiotic-containing formula at levels as high as 1 billion cfu/g (240 g serving) was found to be safe and well tolerated by children.[88, 89]

Along with providing health benefits, BB-12 is a highly sought probiotic because it has a high resistance to acids in fermented dairy products and is aerotolerant.[90] Importantly for our study, it is believed that dairy products provide a protective environment allowing for probiotic bacteria to remain viable through digestion.[90] An issue concerning probiotic delivery in dairy products is a decrease in viable cells by the end of the product's shelf-life. McBearty et al. manufactured a probiotic cheddar cheese containing 10⁸ cfu/ml BB-12.[91] The levels of BB-12 remained constant throughout six months of ripening at a pH of 5.3. Fukushima et al. incorporated BB-12 into an unfermented, canned infant formula.[35] The levels of viable BB-12 cells did not decrease for at least 18 months in the sealed can and for 30 days after the can was opened. BB-12 appears to persist in dairy products; however, the persistence of BB-12 in yogurt, where the pH is lower than 5.0, has not been as widely studied.

Nearly 190 million outpatient antibiotic prescriptions were given in the period of 1998-99. Nearly one quarter (22%) of all pediatric visits resulted in antibiotic prescriptions. A study of 1992 data reported that office visits for colds, upper respiratory tract infections, and bronchitis resulted in approximately 12 million antibiotic prescriptions, accounting for 21% of antibiotic prescriptions.[92] Another study found that antibiotics were prescribed for 78% of acute bronchitis episodes, 65% of acute pharyngitis episodes, 81% of acute sinusitis episodes, and 33% of nonspecific URI episodes, many of which are of viral etiology.[93]

Noncompliance with prescriptions is often due to side effects, most commonly AAD.[94] Diarrhea is a common and costly disease of children in the U.S. Children less than five years of age experience 20-35 million episodes of diarrhea per year. These episodes lead to 2-3.5 million physician visits (which account for 10% of all visits by children), more than 200,000 hospitalizations (13% of hospital admissions in children less than five years), and 325-425 deaths annually.[95-98] There have been many promising studies demonstrating the potential benefits of probiotic supplementation in preventing diarrhea. However, currently, probiotics are generally given in powder, pill or liquid forms and generally sold at health food stores. Yogurt, which is more readily available and accepted, has the potential to greatly influence health if efficacious probiotic dosages and species are available in the product.

This study will evaluate whether a well-defined, probiotic-containing yogurt can be used as an effective delivery vehicle for probiotics. Our long-term goal is to create yogurt with sufficient probiotic dosages to positively impact many different aspects of childhood and adult health. There is widespread acceptance of yogurt with added cultures among the general population and this is one of the reasons we believe yogurt will be more acceptable than supplements.

4.1.9 Summary of Completed Studies

I. Safety of BB-12 Supplemented Strawberry Yogurt For Healthy Adults on Antibiotics:

The primary objective of this Phase 1 study was to establish safety of probiotic BB-12 supplemented yogurt consumed daily for 10 consecutive days by adults concurrently taking antibiotics for an upper respiratory infection. Forty subjects were randomized into two groups, BB-12 supplemented yogurt and control yogurt without BB-12, using the random allocation rule. Forty participants were recruited through Capital Area Primary Care Research Network (CAPRICORN), a practice-based research network. The participants in the study were healthy individuals between the ages of 18-65 years and who were prescribed treatment with a penicillin class antibiotic regimen for an upper respiratory infection. A respiratory infection was classified as any infection the physician designates as strep or non-strep pharyngitis, otitis media, pneumonia, sinusitis or bronchitis that results in a 10-day prescription of antibiotics. All reported adverse events were tabulated by type and treatment group (see **Table 1**). There were no

serious adverse events reported. No participants withdrew from the study due to adverse events.

Table 1. Phase I Adult Study Adverse Events

Event	Control Group (N=21)		BB-12 Group (N=19)	
Event	N	%	N	%
Abdominal pain	1	5	0	0
Acid reflux	0	0	3	16
Allergies (Seasonal, allergic rhinitis)	1	5	0	0
Back pain	0	0	1	5
Bloating	3	14	0	0
Bowel sounds	1	5	0	0
Breathing problems	3	14	0	0
Constipation	3	14	2	11
Cough	8	38	6	32
Decreased appetite	7	33	5	26
Diarrhea	2	10	2	11
Dizziness	0	0	1	5
Drug hypersensitivity	1	5	0	0
Ear aches	5	24	3	16
Fever	2	10	2	11
Gas	6	29	1	5
Headache	7	33	5	26
Irritability	1	5	1	5
Lethargy	8	38	4	21
Loose stool	9	43	4	21
Muscle pain	0	0	1	5
Nasal congestion	7	33	9	47
Nausea	1	5	0	0
Runny nose	7	33	5	26
Sore throat	5	24	6	32
Stomach pain	8	38	3	16
Tonsil swelling	1	5	0	0
Vaginal discomfort	1	5	0	0
Vomiting	0	0	1	5
Yeast infection	0	0	2	11
Total events reported	98		67	

II. Safety of BB-12 Supplemented Strawberry Yogurt For Healthy Children: The primary objective of our Phase 1 pediatric study was to assess the safety of strawberry flavored yogurt supplemented with Bifidobacterium animalis subsp. lactis strain BB-12 when consumed daily for 10 consecutive days by generally healthy children. The secondary objective was to assess the ability of BB-12 to survive gastric transit. The participants in the study were healthy individuals between the ages of 1-5 years. Participants were recruited through CAPRICORN. Twenty-nine participants received the BB-12 yogurt and 31 participants received the control yogurt. All reported adverse events were tabulated by type and treatment group (Table 2). Three serious adverse events were reported (details in Table 2). No participant deaths were reported and no participants withdrew from the study due to adverse events.

Both studies, Safety of BB-12 Supplemented Strawberry Yogurt For Healthy Adults on Antibiotics and Safety of BB-12 Supplemented Strawberry Yogurt For Healthy Children were conducted under the same IND.

Table 2. Phase I Pediatric Study Adverse Events

	Days 0-10			Days 11-180		
	(During Intervention)			(Post-Intervention)		
Event	Control	BB-12	Total	Control	BB-12	Total
Allergies (e.g. seasonal)	1	2	3	1	3	4
Broken finger					1	1
Bronchiolitis					1	1
Cold	2		2	2	1	3
Constipation		3	3	2	1	3
Cough	5	10	15	1	5	6
Croup					1	1
Cut finger				1		1
Diarrhea	2	2	4	2	5	7
Ear aches					1	1
Ear infection				2	1	3
Fever		2	2	2	3	5
Flatulence	2	2	4	1	1	2
Headache				1		1
Hives		1	1			
Irritability	4	1	5	3	5	8
Laceration				1		1
Lack of/decreased appetite	2	2	4	3	1	4
Lethargy	1	5	6			
Loose stool	2	6	8	3	3	6
Lump on back of head				1		1
Nasal congestion	4	6	10		2	2
Pain	2	1	3	2		2
Physical injury				1		1
Pink eye					1	1
Pneumonia					1	1
Rash		2	2	1	2	3
Runny nose	6	12	18	6	9	15
Skin infection				1		1
Sore foot					1	1
Sore throat	1	2	3			
Strep throat					1	1
Umbilical hernia	1		1			
Vomiting		2	2	1	2	3
Total	35	61	96	38	52	90
Serious adverse events ^a		1	1		2	2

^a Serious adverse events included: 1) grade 4/potentially life-threatening fever reported on day 2, 2) grade 4/potentially life-threatening bronchiolitis reported at day 180 and 3) grade 4/potentially life-threatening pneumonia reported at day 180. All serious adverse events were unrelated to the interventions and resolved.

III. The Study to Investigate the Potential of Probiotics (SIPPY I and II): We have also conducted two previous, non-IND but structure/function studies using the same investigational

product, strawberry-flavored BB-12 supplemented yogurt. Both were double-blinded, randomized, placebo-controlled, allocation concealment clinical trials consisting of a combined 354 healthy children between the ages of 1 and 5 years who attended daycare/school at least 3 days per week. The active BB-12 and control products were the same as used in the two Phase I trials. The primary objective was to determine if daily consumption of a probiotic-containing yogurt-based drink for 90 consecutive days decreased absences from daycare for the children, a structure/function outcome. Thus, the total days of BB-12 yogurt consumption was over 30,000 days. There were no significant differences in the days of missed school per group. Importantly there were no differences in adverse events (see **Table 3**) among BB-12 and control groups.

Table 3. SIPPY I and II Adverse Events

SIPPY I Events	Control	BB-12
	N=95	N=87
Number of subjects with at least one adverse event	3	3
Diarrhea	3	2
Pyrexia	0	1
Dermatitis (Diaper)	3	0
Vomiting & Cough (1 participant had 2 adverse events at the same time)	3	0
Hordeolum (Stye)	1	0
Number of subjects with at least one serious adverse event	0	0
SIPPY II Events	Control	BB-12
	N=81	N=91
Number of subjects with at least one adverse event	3	8
Diarrhea	0	2
Hyperactivity	1	0
Rash	0	1
Frequent Stools	1	1
Stomach Pain	2	0
Constipation	0	1
Diaper Rash	0	1
Loose Stools	0	3
Number of subjects with at least one serious adverse event	0	0

4.2 Rationale

The rationale for focusing on food as a vehicle for the transmission of probiotics is that it has the potential to benefit a much larger public health population than using probiotics in a more medicinal manner, such as pills or capsules. Compliance with most medicinal regimens is around 50%; although certain interventions such as simplifying a regimen, collaboration with patients, different formulations, and increased convenience improve compliance.[99-102] We believe a readily available drink containing a high dose of probiotics has the potential to improve compliance through many of these mechanisms. This product also has the potential to positively impact the health of children and adults around the world, as yogurt will likely be more appealing to both children and their parents for long term consumption than pharmaceutical-like preparations. In addition to the benefits associated with the consumption of probiotics, there is an increased health benefit from consuming yogurt, a nutrient dense food.

More specifically, the rationale for this Phase I study is to determine safety of our drink and comply with the FDA's recommendations pertaining to an IND application, we will conduct a phase I safety study.

4.3 Potential Risks and Benefits

4.3.1 Potential Risks

Yogurt: Potential risks and side effects related to the probiotic cultured yogurt include: allergic reaction to drink ingredients, most likely strawberry, or digestive problems such as stomachaches or loose, watery bowels due to lactose intolerance.

There may also be side effects, other than those listed above that we cannot predict. Many side effects may go away shortly after the yogurt consumption is stopped, but in some cases side effects can be serious, long lasting or permanent.

Stool Collection: There is no known risk to stool collection. However, there may be some discomfort with collecting stool samples.

4.3.2 Known Potential Benefits

BB-12: *Bifidobacterium lactis* strain BB-12 is a commercially available probiotic strain used in a number of feeding and clinical trials. Such supplements have shown potential benefits in treatment and prevention of varied diseases including diarrhea, asthma, necrotizing enterocolitis and allergies. It has been also found to significantly improve skin conditions in eczema patients.

Yogurt: Yogurt has its own known benefits coming from milk. For every 6-ounce of serving, there are about 9 grams of animal protein, plus several other nutrients found in dairy foods, like calcium, vitamin B-2, B-12, potassium, and magnesium. Furthermore, yogurt with active cultures is found to help certain gastrointestinal conditions including, lactose intolerance, constipation, and diarrhea.

Yogurt, which is more readily available and accepted by general public, has the potential to greatly influence health if efficacious probiotic dosages and species are available in the product. Therefore, we believe that the benefits of the BB-12 supplemented yogurt far outweigh the discomfort and small risks participants might experience.

5 OBJECTIVES/STATISTICAL METHODS

5.1 Study Objectives

5.1.1 Primary Objective

Objective 1: To test the efficacy of high dose BB-12 supplemented yogurt in preventing AAD, compared to yogurt without BB-12, in children receiving antibiotics.

5.1.2 Secondary Objectives

Objective 2: To assess the safety of yogurt supplemented with BB-12.

Objective 3: To carry out longitudinal community structure and gene expression analysis of fecal microbiota to evaluate the impact of high dose BB-12 in a pediatric population receiving antibiotics.

5.2 Study Outcome Measures

5.2.1 Primary Outcome Measure

The primary outcome is clinically diagnosed diarrhea anytime within 14 days of enrollment. Diarrhea is clinically defined as three or more loose stools per day for two consecutive days. This will be a dichotomous (yes or no) outcome of diarrhea during the 14-day period.

5.2.2 Secondary Outcome Measures

We will be evaluating safety as per FDA regulations on adverse event collection. Parents/caregivers (older children, themselves) will keep a daily diary to track: bowel movements via Bristol scale (see **Appendix**),[103] drink compliance, and adverse events. Secondary outcomes include: duration of diarrhea, respiratory illness duration, a validated pediatric quality of life score for all participants over age 2,[104, 105] stool frequency, stool form measured by Bristol scale,[103] treatment failure (defined as a return to the doctor's office with worsening symptoms), antibiotic compliance, missed school, and missed activities.

6 STUDY DESIGN

This is a randomized, single center, Phase 2 study to test the efficacy of *Bifidobacterium animalis* subsp. *lactis* (*B. lactis*) strain BB-12 (BB-12) yogurt in preventing AAD, compared to yogurt without BB-12, in children receiving antibiotics for a respiratory infection. Three hundred participants will be randomized to two groups, BB-12 supplemented yogurt and control yogurt, using the random allocation rule. This randomization approach will ensure equal allocation of subjects to each group. Participants will be recruited through Capital Area Primary Care Research Network (CAPRICORN), a practice-based research network (PBRN). Children prescribed a 7-10-day penicillin or cephalosporin class antibiotic for a respiratory infection, who meet all the inclusion and exclusion criteria will be enrolled. There will be no exclusion based on race, gender, or insurance status. Based on our previous experience with clinical trials, we will be able to enroll 75 participants in the first year.

7 PARTICIPANTS

7.1 RECRUITMENT STRATEGY

Flyers and posters will also be displayed in all offices participating in the study prior to initiation of the study.

The CAPRICORN research network is specifically designed to help conduct clinical trials. Ideas for studies either come from practicing physicians or University researchers. Regardless of where studies originate, they are then reviewed by the board of directors and sent out to physicians for comment. Thus, not all physicians or offices participate in each study; but are allowed to choose studies that they have interest in and works with their office flow. Because of this grassroots approach, CAPRICORN has been very successful in fulfilling recruitment goals set forth a priori in studies. The network has helped the PI recruit over 1,500 participants in eight randomized controlled trials.

7.2 INCLUSION CRITERIA

We will enroll 300 participants, half for the BB-12 yogurt drink and half for the control yogurt. All parents of children 3-12 prescribed a penicillin or cephalosporin class antibiotic for a respiratory infection will be alerted of the study by their physician or by the study team.

Inclusion: Participants will be eligible if:

- 1. Child is between ages of 3-12
- 2. Caregiver has the ability to read, speak and write English or Spanish
- 3. Household has refrigerator for proper storage of drink
- 4. Household has telephone access
- 5. Enrollment must take place within 24 hours of starting antibiotics
- 6. Outpatient treated
- 7. Treatment with a penicillin or cephalosporin class antibiotic regimen for 7-10 days for a respiratory infection; the following is a list of inclusive antibiotics:
 - a) Amoxicillin
 - b) Augmentin (amoxicillin/clavulanate)
 - c) Ancef (cefazolin)
 - d) Cefadroxil
 - e) Cephalexin
 - f) Cephradine
 - g) Duricef (cefadroxil)
 - h) Keflex (cephalexin)
 - i) Kefzol (cefazolin)
 - j) Velosef (cephradine)
 - k) Ceclor (cefaclor)
 - I) Cefotan
 - m) Cefoxitin
 - n) Ceftin (cefuroxime)
 - o) Cefzil (cefprozil)
 - p) Lorabid (loracarbef)
 - q) Mefoxin (Cefoxitin)
 - r) Zinacef (cefuroxime)
 - s) Omnicef (cefdinir)
 - t) Suprax (cefixime)
 - u) Dicloxacillin
 - v) Pen-Vee K (penicillin)

A respiratory infection will be classified as any infection the physician designates as strep or non-strep pharyngitis, otitis media, pneumonia, sinusitis or bronchitis that results in a prescription of antibiotics.

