9.2 ENROLLMENT/BASELINE

The enrollment/baseline visit will take place at the participants' homes or doctor's office where comfort and confidentiality is assured. The purpose of this visit is to have in-person time to collect baseline data, explain all forms, go over the schedule of visits and intervention, and give the participant the initial compensation.

The enrollment/baseline visit will be completed virtually, when public health guidelines recommend limiting in-person visits or when participants prefer a virtual visit.

Once it is confirmed that the parents/caregivers and child meets all inclusion and exclusion criteria, baseline data will be collected. These include: Baseline Health Status and Demographic Information.

Following the baseline procedures, the parents/caregivers will receive the BB-12 yogurt or control yogurt for days 1 through 7-10 to be given to their child once a day. In addition, they will also receive measuring cups that denote level of 4 ounces. The amount of BB-12 supplemented yogurt drink to be supplied will be 4 ounces per day, which is slightly more than 100 grams/day.

Parents/caregivers will be asked to collect a stool sample from their child prior to starting the yogurt. Stool for children who stool in a toilet will be collected via a stool hat and transferred to proper vials. Stools for children in diapers will be collected directly from the diapers. Stools will be collected multiple times throughout the study. Research staff will be trained on how to properly transport stool and how to instruct participants on collecting stool.

During the initial visit, parents/caregivers will also be given all materials to collect stools, the diary, and study materials as well as the initial compensation.

Following virtual enrollment/baseline visits, study supplies typically delivered at enrollment—prescribed investigational product (yogurt), forms for data collection, and kits for sample collection—will be delivered following the informed consent process and after all required signatures have been obtained.

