9.3 TELEPHONE FOLLOW-UP

On the first day that the participant drinks the yogurt, parents will schedule a phone call for 30 minutes after the drink is consumed, to ensure any adverse events are recorded. Parents will alert study personnel what time their child will consume the first yogurt and study personnel will call the participant 30 minutes after to ensure that there are no side effects from the yogurt.

These follow-up phone visits will be completed on Days 7, 11, 14 and 180 (±2 days). It is imperative that all visits be completed on a timely and regular fashion.

Generally, the Follow-Up Form will be the only form completed during the phone calls, but at times depending on parent/caregiver's report, there may be another form or two.

The follow up period includes all the time previous to the day of the interview. Any incidents that happen the day of the visit would be captured in the next Follow Up Visit.

There will be a set day that each subsequent visit should be completed for each participant. The research personnel should call all parent/caregiver's phone numbers at least one time per day in order to collect the data. If more than 3 business days have passed from the set day, the RA should alert the PI that this week's Follow-Up Form has not yet been completed. If the RA is not able to contact the participant, a Missed Visit Report Form should be completed instead and the PI should be alerted once again.

If a participant is unmasked at any point in time in during the study, PI will be alerted immediately. A Georgetown University employee in the Department of Family Medicine not associated with the study will follow up with this participant from this point on. This particular research personnel is not to discuss any information regarding this occurrence with any other personnel other than the PI.

Additional stool samples will be collected on Days 7, 14, 21 and 30 (±2 days) (Table 8).

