11.4.3 Anticipated Results and Interpretation

The experiments described in this aim will provide us with sequential samples from which data on both microbial composition (based of 16S rRNA profiling) and community function (based on RNASeq data) can be generated. We anticipate that longitudinal 16S rRNA profiling will provide insight into a number of distinct shifts in the microbiota (i.e., loss of particular taxa, loss of overall community diversity) that reflect the impact of antibiotics (control group) and antibiotics plus BB-12 (active yogurt group).

The impact of antibiotic treatment on the microbiota: In this clinical trial, all participants will be treated with a 7-10-day course of antibiotics beginning on day 1, and will be followed for another 20-23 days following cessation of antibiotic therapy. We will assess changes in the microbiota at five time points over this 30-day period. This study design will provide us an opportunity to capture information on antibiotic-induced changes in the microbiota, as well as monitor the recovery of the microbiota in 300 participants. We anticipate that a subset of participants will develop diarrhea, and we will generate data on microbiota changes during the progression from the diarrheal state to the non-diarrheal state. This will allow us to ask if changes in the relative abundance of specific members of the gut microbiota (either alone or in combination) correlate with clinical outcome. To our knowledge, there have been no studies that examine the microbiota during the progression to a diarrheal state and the resolution of the diarrheal state. There have been limited studies on the treatment with antibiotics,[47, 126] but not in the context of disease resolution, nor in a pediatric population. We anticipate these findings will be novel and provide insight into the dynamics of the human gastrointestinal tract.

We will also use the baseline16S rRNA data to identify gut enterotypes in the 300 participants in this clinical trial. With regard to this aspect of data analysis, we will test the hypothesis that specific enterotypes are more/less resistant to development of antibiotic-induced diarrhea and more/less likely to show complete recovery of community structure following antibiotic

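### The baseline stool is guaranteed to be pre-yogurt but not pre-antibiotic, yet the microbiome plan uses it as the reference for antibiotic-induced change, enterotype resistance and recovery

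*Combined protocol and SAP*

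**What the plan says.** All references are to the combined protocol and SAP.

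- Section 7.2, inclusion criterion 5: "Enrollment must take place within 24 hours of starting antibiotics". Section 10.1 counts a child as enrolled when the parent or caregiver signs consent, so this limit ends at consent, not at the stool.
- Section 9.2 on the baseline sample: "Parents/caregivers will be asked to collect a stool sample from their child prior to starting the yogurt". After a virtual visit, the yogurt and sample kits "will be delivered following the informed consent process and after all required signatures have been obtained", with no time limit.
- On Day 1, Section 9.2 says that families "will receive the BB-12 yogurt or control yogurt for days 1 through 7-10", while Section 11.4.3 says that "all participants will be treated with a 7-10-day course of antibiotics beginning on day 1". Table 8 puts the baseline stool at Day 0/1.
- Section 11.4.3 on use of the samples: "This study design will provide us an opportunity to capture information on antibiotic-induced changes in the microbiota"; and "We will also use the baseline16S rRNA data to identify gut enterotypes in the 300 participants in this clinical trial". It then tests whether certain enterotypes resist antibiotic-induced diarrhea or recover more completely.
- Sections 11.4.4 and 11.4.5 compare gene expression at baseline and Day 7, including antibiotic-induced rises in resistance-gene expression.
- Section 9.3 schedules later stools on Days 7, 14, 21 and 30, each within 2 days either way. Courses last 7 to 10 days (Sections 6 and 7.2). Section 11.4.3 states 20 to 23 days of follow-up after antibiotics end.

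**The concern.** The baseline sample has two uses. For BB-12 versus control it must precede the yogurt, and it does. For statements about the antibiotic it should also precede the antibiotic, and nothing ensures that.

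Every child receives an antibiotic, so the within-child baseline is the only reference for antibiotic-induced change, and randomization cannot repair it. If some baselines are already exposed:

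- change from baseline omits whatever shift had already occurred;
- an enterotype assigned after exposure may partly reflect early disturbance, so its association with diarrhea is harder to read as a pre-existing trait;
- recovery to baseline is ambiguous when the baseline is itself perturbed;
- the expression analysis, which has only two time points, loses its unexposed one.

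At the other end, samples scheduled by study day mix children at different times after the end of their course, which blurs any description of recovery after antibiotics stop.

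**Working it through.** **Inputs.** Enrollment lag after first dose: up to 24 h (Section 7.2). Time from consent to baseline stool: not limited (Section 9.2), so assumed below. Course length c: 7 to 10 days (Section 7.2). Sample day s: 7, 14, 21 or 30, within 2 days either way (Section 9.3).

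**1. Reproduce the plan's figure.** Days after the end of the course = s − c. At Day 30: 30 − 10 = 20 and 30 − 7 = 23, which matches the stated 20 to 23. The match needs the antibiotic to start on study Day 1 and the stool to be taken exactly on Day 30.

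**2. Antibiotic exposure permitted before the baseline stool.** Exposure = enrollment lag + time from consent to stool. These are upper limits, not estimates.

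| Assumed time from consent to stool | Maximum exposure | Share of a 10-day to a 7-day course |
|---|---|---|
| none | 24 h | 1/10 = 10% to 1/7 = 14% |
| up to 24 h | 48 h | 2/10 = 20% to 2/7 = 29% |
| up to 48 h | 72 h | 3/10 = 30% to 3/7 = 43% |

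Only the first row rests on the documents alone. The minimum is zero in every row, because a child may enroll before or at the first dose.

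**3. Later samples, antibiotic starting on Day 1.** Earliest = s − 2 − 10; latest = s + 2 − 7. Negative values mean days of the course remaining.

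| Sample | On the exact day (s − 10 to s − 7) | With the 2-day window |
|---|---|---|
| Day 7 | −3 to 0 | −5 to +2 |
| Day 14 | 4 to 7 | 2 to 9 |
| Day 21 | 11 to 14 | 9 to 16 |
| Day 30 | 20 to 23 | 18 to 25 |

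The window ranges pair the extremes of course length and timing. The Day 7 label can cover both on-treatment and off-treatment stools.

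**4. Antibiotic starting one day before study Day 1**, at the enrollment limit. The latest values rise by 1: Day 7 to +3, Day 14 to 10, Day 21 to 17, Day 30 to 26.

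**5. Which analyses are touched.** Antibiotic-induced change, enterotype resistance, recovery after antibiotics end, and baseline-to-Day 7 expression all need an antibiotic anchor. BB-12 versus control needs only a pre-yogurt baseline. The primary outcome, diarrhea within 14 days of enrollment (Section 5.2.1), uses no stool sample as a reference.

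**The case against.** The strongest reply is that Objective 3 (Section 5.1.2) concerns the impact of BB-12, for which the baseline is valid, and that stool timing should be similar across blinded randomized arms. That stands. It confines the point to the antibiotic-effect, enterotype and recovery readings, but Section 11.4.3 sets these out as results in their own right.

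Four stronger readings are tempting, and the documents do not support them.

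- *The samples will be analyzed on nominal days.* Section 11.4.2 names no time variable, and Sections 9.4 and 9.5 put the actual collection date and time on the label. What is missing is a rule tying samples to antibiotic start or stop.
- *Many or most baselines are exposed.* No share is given. Families may be approached as the antibiotic is prescribed (Section 9.1) and enrolled at the doctor's office (Section 9.2), so some stools may precede the first dose.
- *The antibiotic effect is understated by a known amount.* The documents give no figure for how far a day of antibiotic shifts an enterotype or a diversity measure.
- *Every later analysis should use days since last dose.* Actual last dose is post-randomization, and Section 4.1.8 links noncompliance to side effects, chiefly antibiotic-associated diarrhea. If BB-12 affects diarrhea, that time axis could differ by arm and bias a comparison that is otherwise sound.

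**Conclusion.** The concern holds for the uncontrolled antibiotic readings of Aim 3 and no further. The plan permits a baseline stool after up to 24 hours of antibiotic at enrollment, and longer with any delay in kit delivery or in the first stool. It uses that sample as the antibiotic reference without an exposure measure or an analysis rule. How many children are affected, and by how much, cannot be determined from the documents.

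The time since the end of antibiotics at later samples is also wider than the stated follow-up suggests, assuming the antibiotic starts on Day 1 and families use the full window. This is worth correcting because the change is small and these readings have no other reference.

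**What to change.** 1. In Section 11.4.3, call the sample pre-yogurt and state which event Day 1 marks in the microbiome analysis.
2. Record the date and time of the first antibiotic dose. Compute hours from that dose to the baseline stool, and report the share of baselines taken after it.
3. In the antibiotic-change, enterotype and baseline-to-Day 7 expression analyses, include exposure hours as a covariate. Add a sensitivity analysis restricted to stools passed before the first dose or within a short interval after it, with the interval fixed in advance. Keep this as a sensitivity analysis, because stool and delivery timing decide who enters it.
4. Record the date of the last antibiotic dose. For the uncontrolled description of recovery only, use actual days since that dose.
5. For BB-12 versus control, keep scheduled study day, or actual days since randomization, as the time axis.

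**Cost.** No change to treatment or to the sampling schedule. Stool date and time are already on the label. First-dose timing is needed to check criterion 5, but no section shows that it is stored. Section 5.2.2 and Appendix II mention antibiotic compliance and doses completed, not a last-dose date. Both antibiotic dates must therefore be confirmed as captured. The restricted analysis will have fewer children, most noticeably for expression, where Section 11.4.4 expects only about 50 participants.
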